9.0 Study Drug Duration and Compliance

There is no study drug dispensed in this study.

10.0 Efficacy Analyses

10.1 General Considerations

General Considerations

Plasma HCV RNA levels will be determined for each sample collected by the central laboratory using the Roche COBAS® AmpliPrep/COBAS® TaqMan® HCV Quantitative Test, v2.0. The lower limit of detection (LLOD) and lower limit of quantification (LLOQ) for this assay (regardless of genotype) are both 15 IU/mL.

HCV RNA results that are detectable but not quantifiable are reported as "< 15 IU/ML HCV RNA DETECTED" and those that are undetectable are reported as "HCV RNA NOT DETECTED" in the database.

The notation "HCV RNA < LLOQ" is used to represent all HCV RNA values < 15 IU/mL, including values reported as "HCV RNA NOT DETECTED" or "< 15 IU/ML HCV RNA DETECTED." HCV RNA ≥ LLOQ are all quantifiable values of 15 IU/mL or greater.

IL28B rs12979860 will be resulted as C/C, C/T, or T/T by the central laboratory in the previous study.

Definitions for Efficacy Endpoints

A confirmed quantifiable post-treatment value is defined as any two consecutive post-treatment HCV RNA measurements \geq LLOQ. In all relapse analyses, completion of treatment is defined as study drug duration \geq 52 days for 8-week regimens, \geq 77 days for 12-week regimens, and \geq 105 days for 16-week regimens.

ABT-493/ABT-530
M13-576 – Statistical Analysis Plan
Version 1.0 – 23 Aug 2019

 SVR_4 = HCV RNA < LLOQ in the SVR_4 window (4 weeks after the last actual dose of study drug) without any confirmed quantifiable (\geq LLOQ) post-treatment value before or during that SVR window (derived from the previous study).

 SVR_{12} = HCV RNA < LLOQ in the SVR_{12} window (12 weeks after the last actual dose of study drug) without any confirmed quantifiable (\geq LLOQ) post-treatment value before or during that SVR window (derived from the previous study).

[figure not shown]
SVR₂₄ = HCV RNA < LLOQ in the SVR₂₄ window (24 weeks after the last actual dose of study drug) without any confirmed quantifiable (\geq LLOQ) post-treatment value before or during that SVR window (derived from the previous study).

Relapse₁₂ = confirmed HCV RNA \geq LLOQ between end of treatment and 12 weeks after last actual dose of study drug (up to and including the SVR₁₂ assessment time point) for a subject with HCV RNA < LLOQ at Final Treatment Visit who completed treatment (defined above based on study drug duration in the previous study), excluding reinfection (derived from the previous study).

Relapse_{late} = confirmed HCV RNA \geq LLOQ at any time after the SVR₁₂ assessment time point for a subject who achieved SVR₁₂ and has post-SVR₁₂ HCV RNA data available, excluding reinfection (derived from both studies).

Relapse_{overall} = confirmed HCV RNA ≥ LLOQ between end of treatment and up to and including the last HCV RNA measurement collected in Study M13-576 for a subject with HCV RNA < LLOQ at Final Treatment Visit who completed treatment, excluding reinfection.

 $SVR_{overall}$ = HCV RNA < LLOQ between the end of treatment and up to and including the last HCV RNA measurement collected in Study M13-576 without any confirmed quantifiable (\geq LLOQ) post-treatment value before value.

Only subjects who have at least one post-treatment HCV RNA value will be included in analyses of relapse. If the last available post-treatment value is \geq LLOQ, then the subject will be considered a relapse (i.e., will not require confirmation).

[figure not shown]
HCV reinfection is defined as confirmed HCV RNA ≥ LLOQ after the end of treatment in a subject who had HCV RNA < LLOQ at Final Treatment Visit, along with the post treatment detection of a different HCV genotype, subtype, or clade compared with baseline, as determined by phylogenetic analysis of the NS3 or NS5A, and/or NS5B gene sequences. Reinfection in the case of the same HCV subtype is defined as a clade switch, as indicated by the lack of clustering between the baseline and post-treatment sequences by phylogenetic analysis. If phylogenetic analysis is not possible due to technical difficulties, HCV reinfection may be determined with a confirmed HCV genotype or subgenotype switch by the Versant HCV Genotype Inno-LiPA Assay v2.0 or Sanger assay.

Post-treatment relapse is defined as described earlier (**Relapse**₁₂, **Relapse**_{late}, **Relapse**_{overall}), and no genotype, subtype, or clade switch compared with baseline as determined by phylogenetic analysis of the NS3 or NS5A gene sequences. If phylogenetic analysis is not possible due to technical difficulties, the subject will be defined as having a post-treatment relapse unless an HCV genotype or subgenotype switch is confirmed by the Versant HCV Genotype Inno-LiPA Assay v2.0 or Sanger assay.

In the efficacy analyses, SVR₁₂ and Relapse₁₂ will be based on the values from the previous study. Relapse_{late}, Relapse_{overall} and SVR_{overall} will be derived based on HCV RNA data collected both in the previous study and in this study. Subjects with reinfection will be identified using data from both studies.

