10.2 Efficacy Analyses

The following efficacy analyses will be conducted on the full analysis set including data up to the last follow-up in this study prior to any HCV re-treatment. For subjects in the

[figure not shown]

full analysis set, HCV RNA measurements taken after the start of another anti-viral HCV treatment (after completion of AbbVie DAA treatments in previous study) will be excluded from the analyses.

The number and percentage of subjects in the full analysis set who achieved SVR₁₂ in the previous study will be summarized overall and by study. A listing of subjects in the full analysis set who did not achieve SVR₁₂ will be provided.

Based on the full analysis set, the number and percentage of subjects who maintain SVR in this study among those who achieved SVR₁₂ in the previous study will be summarized, overall and by visit. Study visits will be displayed as Post-Treatment Weeks 24, 36, 48, 60, 72, 84, 96, 108, 120, 132, 144, and 156. For each visit, the denominator will indicate the number of subjects in the full analysis set who achieved SVR₁₂ and have HCV RNA data within the corresponding visit window. For the overall summary, the denominator will indicate the number of subjects in the full analysis set who achieved SVR₁₂. Overall maintenance of SVR is defined as no confirmed HCV RNA ≥ LLOQ after the SVR₁₂ timepoint (from the previous study) through the last HCV RNA measurement in this study. Confirmation of quantifiable HCV RNA values can occur among any two consecutive HCV RNA values; either both during the same visit window or at the end of a visit window and in the next window. The visit window corresponding to the first occurrence of the confirmed HCV RNA ≥ LLOQ will be counted as having the failure. If the last available value in the study is \geq LLOQ, then the subject will be considered as not maintaining SVR (i.e., will not require confirmation). The summary will include the subject number and the visit window corresponding to the first occurrence of quantifiable HCV RNA.

Among the subjects in the full analysis set who achieved SVR₁₂ in the previous study, a listing of subjects who do not maintain SVR will be provided with subject number, previous study number, the reason (relapse or reinfection) for not maintaining SVR, days from study drug end date to relapse or reinfection, and whether the relapse or reinfection occurs before or after enrolling into this study.

[figure not shown]

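### SAP 10.1 waives confirmation of a last quantifiable HCV RNA value for relapse but not for reinfection, which leaves one pattern without a consistent label

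*SAP*

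**What the plan says.** The relevant rules are all in SAP 10.1 and 10.2.

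- **Confirmation (10.1).** "A confirmed quantifiable post-treatment value is defined as any two consecutive post-treatment HCV RNA measurements" at or above the LLOQ, which is 15 IU/mL.
- **Last value (10.1).** If the last available post-treatment value is quantifiable, "then the subject will be considered a relapse (i.e., will not require confirmation". The sentence makes no exception for a change of genotype, subtype or clade (below, a switch).
- **Reinfection (10.1).** "HCV reinfection is defined as confirmed HCV RNA ≥ LLOQ after the end of treatment in a subject who had HCV RNA < LLOQ" at the Final Treatment Visit, together with a switch from baseline. There is no last-value exception.
- **Relapse (10.1).** Relapse_late and Relapse_overall both exclude reinfection. A later paragraph adds a further condition: "and no genotype, subtype, or clade switch compared with baseline as determined by phylogenetic analysis of the NS3 or NS5A gene sequences". Where that analysis is technically impossible, "the subject will be defined as having a post-treatment relapse unless an HCV genotype or subgenotype switch is confirmed" by the LiPA or Sanger assay.
- **Reporting (10.2).** A quantifiable last value counts as not maintaining SVR, again without confirmation. Each SVR12 subject who does not maintain SVR is listed with "the reason (relapse or reinfection) for not maintaining SVR". The Kaplan-Meier summaries are split into relapse and reinfection using the 10.1 definitions.

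**The concern.** The waiver was written for one outcome only, although a single quantifiable last value can arise from either. The evidence that separates the two can exist without a second sample. Protocol Appendix C, Table A, schedules a resistance sample at every visit alongside HCV RNA, and SAP 10.3 sends subjects who become viraemic during the study for sequencing without requiring confirmation. A switch can therefore be documented from one visit while the SAP gives no coherent way to use it.

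The distinction matters because relapse speaks to the durability of the drug effect and reinfection does not. SAP 12.0 names relapse and maintenance of SVR as the outcomes of main interest. Protocol 8.1.1 asks for the two kinds of event to be separated by sequence evaluation and does not make RNA confirmation a condition for new infection. The SAP's list of changes from the protocol does not mention the added condition.

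**Working it through.** The plan states no figure to reproduce: the study is descriptive, with no sample size calculation and no hypothesis test. The check has two parts.

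**1. Do the definitions cover every viraemic pattern?** Three facts decide the label: whether the quantifiable value is confirmed, whether the last value is quantifiable, and whether a switch is shown. Leaving out subjects with neither a confirmed nor a last quantifiable value gives six patterns.

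| Confirmed | Last value ≥ LLOQ | Switch | Reinfection | Relapse: last-value sentence, reinfection excluded | Relapse: no-switch condition applied |
|---|---|---|---|---|---|
| No | Yes | No | No | Yes | Yes |
| **No** | **Yes** | **Yes** | **No** | **Yes** | **No** |
| Yes | No | No | No | Yes | Yes |
| Yes | No | Yes | Yes | No | No |
| Yes | Yes | No | No | Yes | Yes |
| Yes | Yes | Yes | Yes | No | No |

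All six count as not maintaining SVR. Five receive exactly one label on either reading. The second row does not. Excluding reinfection from relapse does not help there, because an unconfirmed value never meets the reinfection definition. If the no-switch condition governs, the subject has no label. The subject then still needs a listed reason, and under the Kaplan-Meier rule in 10.2 would be censored on the date of the positive sample.

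**2. How much can one subject move the result?** The documents give about 400 subjects enrolled in total (SAP 4.2) and an attempt to enrol all virologic failures not being immediately re-treated with the same drugs. They do not give the number with SVR12, so denominators of 200, 300 and 400 are assumptions.

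Shift from one subject = 100 × 1/n:

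- n = 400: 100/400 = 0.25 points
- n = 300: 100/300 = 0.33 points
- n = 200: 100/200 = 0.50 points

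For context, exact (Clopper-Pearson) 95% intervals use the beta quantiles B(0.025; x, n−x+1) and B(0.975; x+1, n−x), with lower limit 0 when x = 0:

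| Assumed n | 0 late relapses | 1 late relapse |
|---|---|---|
| 400 | 0% (0 to 0.92) | 0.25% (0.01 to 1.38) |
| 300 | 0% (0 to 1.22) | 0.33% (0.01 to 1.84) |
| 200 | 0% (0 to 1.83) | 0.50% (0.01 to 2.75) |

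If no other late relapse occurred, one such subject would decide whether the study reports none or one.

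**The case against.** The strongest reply is that the last-value sentence explains itself: it may waive only the word *confirmed* and leave the other relapse conditions, including the absence of a switch, in force. On that reading a documented reinfection is not relabelled as relapse. This is a fair reading, but it puts the subject in neither category while 10.2 demands one, so a defect remains.

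It does defeat a stronger inference that a reader might draw: that the rule moves events systematically from reinfection to relapse and so understates durability. That direction follows from only one of the two readings.

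A reader might also infer that any reinfection first seen at a final visit is caught. The documents do not support that. Protocol 5.3.1.1 (HCV RNA Levels) says a change to quantifiable RNA should be retested no later than 2 weeks after the visit, and a positive retest confirms the value. The gap needs a missed retest, loss to follow-up, or re-treatment before confirmation, since SAP 6.3 excludes values from the start of new treatment. The switch must also be documented. Only samples of at least 1,000 IU/mL are sequenced, so a lower last value would usually default to relapse with or without a change to the rule.

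The reporting consequences are limited too. Overall maintenance of SVR is the same either way. The second primary variable in Protocol 5.3.2 combines relapse and new infection, so swapping one label for the other leaves its total unchanged. The individual listings would make an odd case visible. All of this narrows the point. None of it supplies the missing label.

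**Conclusion.** The inconsistency is real and confined to one pattern: an unconfirmed last quantifiable value with a documented switch. It can alter the Relapse_late and Relapse_overall percentages, the reinfection count, the listed reason and the separate Kaplan-Meier curves. It does not alter overall maintenance of SVR, nor the combined relapse-or-new-infection total provided the subject is given one of the two labels.

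The size is 0.25 to 0.50 percentage points of late relapse per subject, which rests on the assumed SVR12 denominators. The documents give no basis for a precise denominator, for the number of late events, or for how often the pattern will occur; it should be rare. The change is still worth making, because the rules contradict each other on a separately reported outcome, few events may be available to absorb an error, and the data needed are already collected.

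**What to change.** In SAP 10.1, replace the last-value sentence with a rule that covers both outcomes, for example:

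*A quantifiable last available post-treatment value needs no confirmation for either relapse or reinfection. All other conditions of the relevant definition continue to apply (HCV RNA below LLOQ at the Final Treatment Visit, and completion of treatment or achievement of SVR12 as applicable). The event is a reinfection if phylogenetic analysis, or the LiPA or Sanger fallback, shows a switch from baseline. Otherwise it is a relapse, including when no sequence or genotype result is available.*

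Add a matching exception to the reinfection definition, so that its requirement for confirmed RNA does not contradict the new rule. All six patterns then receive exactly one label, and the SAP's existing relapse default is kept. The cost is a few sentences in the SAP and the matching line of derivation code. No new data, samples or visits are needed.

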10.2 Efficacy Analyses

The following efficacy analyses will be conducted on the full analysis set including data up to the last follow-up in this study prior to any HCV re-treatment. For subjects in the

[figure not shown]

full analysis set, HCV RNA measurements taken after the start of another anti-viral HCV treatment (after completion of AbbVie DAA treatments in previous study) will be excluded from the analyses.

The number and percentage of subjects in the full analysis set who achieved SVR₁₂ in the previous study will be summarized overall and by study. A listing of subjects in the full analysis set who did not achieve SVR₁₂ will be provided.

Based on the full analysis set, the number and percentage of subjects who maintain SVR in this study among those who achieved SVR₁₂ in the previous study will be summarized, overall and by visit. Study visits will be displayed as Post-Treatment Weeks 24, 36, 48, 60, 72, 84, 96, 108, 120, 132, 144, and 156. For each visit, the denominator will indicate the number of subjects in the full analysis set who achieved SVR₁₂ and have HCV RNA data within the corresponding visit window. For the overall summary, the denominator will indicate the number of subjects in the full analysis set who achieved SVR₁₂. Overall maintenance of SVR is defined as no confirmed HCV RNA ≥ LLOQ after the SVR₁₂ timepoint (from the previous study) through the last HCV RNA measurement in this study. Confirmation of quantifiable HCV RNA values can occur among any two consecutive HCV RNA values; either both during the same visit window or at the end of a visit window and in the next window. The visit window corresponding to the first occurrence of the confirmed HCV RNA ≥ LLOQ will be counted as having the failure. If the last available value in the study is \geq LLOQ, then the subject will be considered as not maintaining SVR (i.e., will not require confirmation). The summary will include the subject number and the visit window corresponding to the first occurrence of quantifiable HCV RNA.

Among the subjects in the full analysis set who achieved SVR₁₂ in the previous study, a listing of subjects who do not maintain SVR will be provided with subject number, previous study number, the reason (relapse or reinfection) for not maintaining SVR, days from study drug end date to relapse or reinfection, and whether the relapse or reinfection occurs before or after enrolling into this study.

[figure not shown]
The number and percentage of subjects who relapse (see **Relapse**_{late} definition) at any time up to the last follow-up in this study will be summarized out of subjects in the full analysis set who achieved SVR₁₂ in the previous study. In addition, the number and percentage of subjects in the full analysis set who relapsed anytime (see **Relapse**_{overall} definition) or have new HCV infection (see definition of reinfection) anytime will be summarized.

The time to relapse (**Relapse**_{overall}) or new HCV infection (i.e., reinfection) from the end of DAA treatment for subjects who achieved HCV RNA < LLOQ at the end of treatment in the previous study will be displayed graphically using Kaplan-Meier curves. Similarly, the time to relapse (**Relapse**_{late}) or new HCV infection (i.e., reinfection) from the SVR₁₂ time point for the subset of subjects who achieved SVR₁₂ in the previous study will also be displayed graphically using Kaplan-Meier curves. These summaries will be separate for subjects who have probable relapse as distinguished from subjects who have probable new HCV infection (i.e., reinfection) based on the definitions of relapse and reinfection in Section 10.1.

For the first Kaplan-Meier curve among subjects with final on-treatment HCV RNA < LLOQ, time to event will be measured as the number of days from the last dose of study drug (in the previous study) to event or censoring time. Subjects who do not relapse or were not reinfected will be censored at the date corresponding to the last available HCV RNA measurement.

For the second Kaplan-Meier curve among subjects who had achieved SVR₁₂, time to event will be measured as the number of days from the nominal day of SVR₁₂ assessment to event or censoring time. Subjects who do not relapse or were not reinfected will be censored at the date corresponding to the last available HCV RNA measurement.

For both subjects in the full analysis set and subjects excluded from the full analysis set, a listing of subjects who are re-treated will be provided specifying whether the re-treatment occurs before or after enrolling into the study, prior AbbVie regimen, HCV re-treatment regimen, and SVR₁₂ outcome.

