### **5.2.3 Prior and Concomitant Therapy**

The HCV drug treatment regimen and its duration given as a part of the subject's participation in the prior AbbVie HCV study, as well as all other past HCV treatment regimens and their durations received by the subject, will be recorded in the eCRF. Commercially available prescription medications for the treatment of HCV therapy, including regimens containing commercially available glecaprevir/pibrentasvir (GLE/PIB,

investigationally known as ABT-493/ABT-530), initiated after the completion of a subject's participation in the previous clinical study (either prior to or during participation in this study) are permitted, and the regimen received and duration will be recorded in the eCRF. Subjects enrolled with virologic failure who undergo re-treatment with a HCV antiviral regimen not containing investigational ABT-493/ABT-530 will be followed until completing the post-treatment Week 12 visit after receiving their re-treatment regimen, after which they will discontinue from the study. If a subject with virologic failure is enrolled into this study and later enrolls in the AbbVie Study M15-942, such subjects will discontinue from Study M13-576.

The use of investigational medications is not allowed during participation in this study. Subjects who are enrolled in the Study M13-576 and who take an investigational medicine as a participant in a separate trial will be required to discontinue participation in the Study M13-576.

Information regarding medication or vaccine use (including over-the-counter medications, vitamins, and/or herbal supplements) will not be collected in this study with the exception of:

- Prescription medications taken for the treatment of HCV since the completion or discontinuation of the previous clinical study (either prior to or during this study).
- Any medications taken for treatment of an SAE as defined in Section 6.0.

This information will be collected at each study visit and will be recorded in the electronic case report form (eCRF). The medication name along with the reason for use, date(s) of administration including start and end dates, and dosage information including dose, route and frequency will be recorded.

The AbbVie Therapeutic Area Medical Director should be contacted if there are any questions regarding concomitant or prior therapy(ies).

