## **5.6 Discussion and Justification of Study Design**

### **5.6.1 Discussion of Study Design and Choice of Control Groups**

This is a rollover study to assess resistance and durability of response to ABT-493 and/or ABT-530 in subjects who have participated in Phase 2 or 3 clinical studies with these agents for the treatment of chronic HCV. No AbbVie study drug will be administered in this study. As such, the absence of randomization, blinding or control groups is appropriate. No quantitative analyses or tests of statistical significance are planned; statistical analyses will be purely descriptive.

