4.2 Study Design

This Phase 2/3, multicenter study will be conducted in subjects who received at least one dose of an ABT-493- and/or ABT-530-containing regimen at any dose level in a prior AbbVie Phase 2 or 3 study for the treatment of chronic HCV and elect to enroll in this study. The subject must have completed the follow-up period of the prior eligible AbbVie study. It is anticipated that approximately 400 subjects will participate in this study. An attempt will be made to enroll all virologic failures who will not receive immediate retreatment with a regimen containing ABT-493/ABT-530.

At the Day 1 Visit, subjects will provide written (signed and dated) informed consent prior to any study specific procedures being performed. The investigator will evaluate whether the subject meets all of the eligibility criteria prior to enrollment in this rollover study. Subjects will be followed for approximately 3 years following their last dose of DAA in the previous AbbVie HCV clinical study; the 3 years will be inclusive of any post-treatment period in the prior study, as well as any gap between the end of the prior study and enrollment into this study. Once a subject has reached 3 years post-DAA therapy, participation in this study will be completed, except for subjects enrolled with virologic failure who receive re-treatment with a new HCV antiviral regimen that does not contain ABT-493/ABT-530. Subjects who are re-treated with HCV regimens other than ABT-493/ABT-530 will have only one further assessment for treatment outcome 12 weeks after stopping that therapy or earlier in cases of virologic failure. Subjects who have not been re-treated will return to the study site for their scheduled visits on an outpatient basis as described in Section 5.3.1 of the protocol until approximately 3 years after their last dose of DAA in the previous clinical study.

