4.3 Sample Size

No sample size determination was conducted for this study. The objective of the study is to characterize the persistence of amino acid substitutions in subjects enrolled in AbbVie DAA studies who experienced virologic failure, and the durability of response in subjects who achieved SVR₁₂. Thus, the number of subjects enrolled in the current trial will be partially based on the number of subjects who experienced virologic failure in prior studies with AbbVie DAA therapies and subsequently agree to participate in the current trial.

The sample size was increased under protocol Amendment 2 to allow for inclusion of a representative sample of subjects from additional studies added in Amendment 2.

[figure not shown]

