6.3 Missing Data Imputation

The values of SVR₄, SVR₁₂, and SVR₂₄ will be derived from the previous study as needed

For subjects in the full analysis set, if a subject starts another treatment for HCV, then all HCV RNA values for this subject measured on or after the start date of the new HCV treatment will be excluded from the analyses of SVR and virologic failure. The subject will be considered a failure for summaries of viral response at all time points after the start of the new HCV treatment.

Missing Data Imputation for Virologic Failure

If HCV RNA values from the central laboratory are missing but a local laboratory value is present in the appropriate time period, then the local laboratory value will be used to assess post-treatment relapse.

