6.4 Overall Type-I Error Control

There is no hypothesis testing for the efficacy analyses, therefore no multiplicity adjustment will be performed for the study.

7.0 Demographics, Baseline Characteristics, Medical History, and Previous/Concomitant Medications

Demographics, baseline characteristics, medical history, and previous/concomitant medications will be summarized on the full analysis set, unless otherwise specified.

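### SAP 10.2 and SAP 6.3 treat re-treated SVR12 subjects differently, so the by-visit maintained-SVR percentage can rise after failures; separately, the overall percentage takes no account of follow-up length

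*SAP*

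**What the plan says.** **By-visit summary (SAP 10.2).** Among subjects with SVR12, maintained SVR is shown at Post-Treatment Weeks 24 to 156. Each row's denominator is limited to those who "have HCV RNA data within the corresponding visit window". A failure is assigned to the window of its first occurrence, and no carry-forward to later windows is stated. The same section excludes "HCV RNA measurements taken after the start of another anti-viral HCV treatment".

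**Re-treated subjects (SAP 6.3).** HCV RNA on or after the start of new treatment is again excluded, but a status is then assigned: "The subject will be considered a failure for summaries of viral response at all time points after the start of the new HCV treatment".

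**Overall summary (SAP 10.2).** The denominator is every full-analysis-set subject with SVR12. Maintained means no confirmed value at or above LLOQ from SVR12 through the subject's last measurement. A last value at or above LLOQ counts as failure without confirmation. No minimum follow-up is required.

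**Data after failure (protocol).** Section 5.3.1.1 stops HCV RNA sampling when re-treatment starts. Appendix C Table B, which re-treated virologic failures then follow, lists no HCV RNA sample. Section 5.2.3 says of virologic failures who enter the separate re-treatment study that "such subjects will discontinue from Study M13-576".

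**Related outputs.** SAP 10.2 also plans a listing of subjects not maintaining SVR, and Kaplan-Meier curves censored at the last HCV RNA value. SAP 8.0 summarises duration of follow-up and discontinuations.

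**The concern.** Take an SVR12 subject who relapses and is then re-treated. Under SAP 10.2 the subject has no usable HCV RNA in later windows and so leaves both numerator and denominator. Under SAP 6.3 the subject stays in as a failure. Two programmers working from the same SAP could produce different tables. Under the 10.2 reading, a durability percentage can go up after failures have occurred.

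The conflict also reaches the overall figure in one case. A subject who starts new HCV treatment with no quantifiable study value is a failure under 6.3, yet meets the 10.2 definition of maintained.

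The overall figure has a second, separate weakness. Each subject is judged only up to his or her own last sample, so someone lost early without viremia counts the same as someone followed for about 3 years. Maintained SVR is the first primary efficacy variable (protocol 5.3.2), so both points bear on how the main durability result is read.

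**Working it through.** **Inputs.** There is no planned figure to reproduce: "No sample size determination was conducted for this study", and "There is no hypothesis testing for the efficacy analyses". The only size given is "It is anticipated that approximately 400 subjects will participate in this study", which includes virologic failures. The documents give no expected failure or loss rate. The following are therefore assumptions, shown as ranges:

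- N = 200 to 400 SVR12 subjects
- k = 1 to 6 failures, each re-treated before the next window
- 50% to 100% of subjects sampled per window, falling by 30% by Week 156
- d = 0 to 40% of subjects lost

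**Step 1: by-visit percentage under the two rules.** Let n be the subjects with usable data in the window, f the new failures, and p the earlier failures already re-treated.

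- SAP 10.2: (n − f) / n
- SAP 6.3: (n − f) / (n + p)

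Example: N = 300, all sampled at Week 24, and one failure each at Weeks 24, 48 and 72.

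| Week | n | f | p | SAP 10.2 | SAP 6.3 |
|---|---|---|---|---|---|
| 24 | 300 | 1 | 0 | 299/300 = 99.67% | 299/300 = 99.67% |
| 36 | 292 | 0 | 1 | 292/292 = 100% | 292/293 = 99.66% |
| 48 | 284 | 1 | 1 | 283/284 = 99.65% | 283/285 = 99.30% |
| 72 | 267 | 1 | 2 | 266/267 = 99.63% | 266/269 = 98.88% |
| 156 | 210 | 0 | 3 | 210/210 = 100% | 210/213 = 98.59% |

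Over the whole assumed range, Week 156 is 100% under 10.2. Under 6.3 it runs from 70/76 = 92.1% (N = 200, k = 6, half sampled) to 280/281 = 99.6% (N = 400, k = 1, all sampled).

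**Step 2: applying 6.3 to the by-visit table brings its own bias.** Scheduled visits are 6 months apart after Month 6 (protocol Appendix C), but the SAP Table 1 windows are 84 days wide. A subject whose Day 1 falls on study drug end day 365 would be sampled at about days 365, 456, 547, 730, 912 and 1095. Those dates fill windows 48, 60, 84, 108, 132 and 156 and leave 72, 96, 120 and 144 empty. Carried-forward failures would sit in every later denominator, while non-failures count only when sampled. If half the subjects have a sample, the example gives 105/(105 + 3) = 97.22% at Week 156, against an overall 1 − 3/300 = 99.00%. The failure share becomes 2.78% instead of 1.00%.

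**Step 3: overall percentage and loss to follow-up.** As planned it is 1 − k/N, which does not depend on d. If lost subjects would have failed at the same rate as the others, and all are removed from the start, it is 1 − k/[N(1 − d)].

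- N = 300, k = 3, d = 30%: 99.00% as planned; 1 − 3/210 = 98.57% with lost subjects removed.
- Largest gap in the range (N = 200, k = 6, d = 40%): 97.0% as planned; 1 − 6/120 = 95.0%, a gap of 2.0 points.
- Counting every lost subject as a failure gives 1 − (3 + 90)/300 = 69.0% in the first case. This is an extreme bound, not an estimate.

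**Step 4: precision.** Assume 380 SVR12 subjects and 4 failures. The overall figure is 376/380 = 98.9%. The exact 95% interval for the failure proportion is 0.29% to 2.67%. With 0/380 the upper limit is 0.97%. The plan reports neither interval.

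**The case against.** The strongest reply is that the primary result is sound. The protocol's primary variable is the overall percentage (5.3.2 and 8.1.1), and the by-visit display appears only in the SAP. A reader might infer that failures vanish from the primary endpoint. They do not: an observed failure counts in the overall figure whenever it occurs, and 376/380 is exactly what the SAP's overall row would show. Each failing subject and the window of first failure are also identified. This stands.

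A reader might also infer that the by-visit rate always goes back to 100%. That needs a window with no new failure and every earlier failure re-treated or gone. Subjects who remain viremic and untreated stay on Appendix C Table A and are sampled at every visit. Nor does the conflict with SAP 6.3 extend to subjects who simply leave, because 6.3 sets no rule for them.

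Unequal follow-up is partly covered by the censored Kaplan-Meier curves and the summary of follow-up duration. The SAP does not call the overall rate a 3-year rate. However, the curves are planned only as graphs, with no tabulated estimate or interval.

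The protocol says "statistical analyses will be purely descriptive", so intervals may look like a preference. That statement excludes tests, and a confidence interval can serve description. Still, leaving intervals out is a gap in reporting and not an error.

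Finally, restricting the overall figure to subjects with a post-SVR12 value would change little. HCV RNA is drawn at Day 1, after the prior study's post-treatment period, so a subject who leaves just after Day 1 would normally still count as maintained.

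**Conclusion.** The concern holds in a limited form. SAP 10.2 and 6.3 give different by-visit tables for re-treated SVR12 subjects, and different overall status for anyone re-treated without a quantifiable value. No text settles either. In the assumed range, Week 156 is 100% under one rule and 92.1% to 99.6% under the other, although the lower end partly reflects the sampling artefact in Step 2. Neither version of the by-visit table measures cumulative durability well.

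The overall percentage keeps all observed failures. Its weakness is unobserved follow-up, worth at most 2.0 points over the assumed range if lost subjects fail at the same rate as others. The documents do not support reading it as grossly inflated; that would require lost subjects to fail far more often than those who stay.

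All values of N, failures, sampling and loss, including the case of 380 subjects with 4 failures, are assumptions. The conflict between the two sections does not depend on them.

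**What to change.** 1. **State one rule for re-treated subjects in SAP 10.2, and cross-refer to it in 6.3.** It should cover both the by-visit and the overall summary. One workable wording is that a subject contributes HCV RNA to the by-visit table up to the start of new treatment, and that the 6.3 failure status applies to the overall summary and not to the by-visit rows. It must say explicitly how a subject re-treated without a quantifiable value is counted, and the number of such subjects should be shown.
2. **Label the by-visit table** as observed data among subjects sampled in that window. Do not add earlier failures to denominators that otherwise hold only sampled subjects.
3. **Tabulate the planned Kaplan-Meier analysis from SVR12** at about Post-Treatment Weeks 48, 96 and 144/156, with 95% confidence intervals and numbers at risk. Show any loss of SVR, and relapse and reinfection separately. This keeps re-treated failures in the cumulative estimate and accounts for unequal follow-up.
4. **Place it beside the overall percentage**, with an exact (Clopper-Pearson) 95% interval.

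The cost is SAP wording and minor programming, with no new data collection. Late durability figures may be slightly less favourable than the by-visit rows would suggest.
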